### 5.7 Quantitative baseline data

Descriptive data about the women who are participating in the research will be collected by the researcher from the woman and recorded on a paper case report form.

- Year of birth
- Length of time pessary used for
- Type and size of pessary in situ
- Comorbidities
- Self-management status
- Self-management experience
- Self-management willingness
- Ethnicity
- Post code
- Level of education
- Female Genital Self-Image Score (FGSIS)

### 5.8 Quantitative phase data collection

Data collection will be completion of a questionnaire which requests information about the woman's demographics, pessary use, self-management experience, willingness to self-manage and a free text box to express thoughts about pessary self-management. Women will also be asked to complete the Female Genital Self-Image Scale (FGSIS-4), a reliable and validated 4-item questionnaire which measures women's attitude and beliefs about their genitals (Herbenick and Reece, 2010).

### 5.9 Quantitative phase sample size

The distribution between willingness to self-manage a pessary and FGSIS-4 has not yet been established. Therefore, based upon statistical advice we have calculated the sample size for a medium effect size of 0.3, for a chi squared test on a two by two table (self-management vs FGSIS). With 5% significance level a sample of 90 will have 80% power to detect a medium effect size of 0.3 (Cohen, 1988). Therefore, based upon this, we aim to recruit 90 women to the quantitative phase.

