### 4.1. Mixed methods methodology

Utilising a mixture of both qualitative and quantitative research through triangulation offers the opportunity to collaborate, elaborate or initiate findings (Rossman and Wilson, 1985). Collaboration refers to the convergence of findings collected via different methodological approaches to test reliability, elaboration is the generation of rich data to expand upon initial findings and initiation, the provocation of further thinking and questioning of findings (Rossman and Wilson, 1985). A mixed methods approach has been chosen to explore the factors which affect willingness to self-manage a pessary for POP with the aim of collecting rich accounts of women's lived experience of being a woman and how that affects their using a pessary for pelvic organ prolapse and their thoughts and experiences of pessary self-management. An explanatory mixed methods approach will enable the researcher to collect data from a large group of pessary using women which can be analysed to explore whether demographics, patient characteristics or self-image of the genitals is correlated with willingness to self-manage a pessary for prolapse. The findings of the quantitative phase will inform the qualitative phases by providing details about a group of women of varying characteristics and opinions about self-management who can then be sampled for the interviews to ensure stratified random sampling. Furthermore, findings of the quantitative phase which affect willingness to self-manage a pessary can be explored in greater detail during interviews as part of the qualitative phase. For example, if it is identified that

What affects willingness to self-manage a pessary? - Protocol Version 1.10 04.08.22

older women completing the questionnaire are less likely to be willing to self-manage their pessary, this will inform the questions to be asked. Moreover, offering women who may not feel comfortable being interviewed the opportunity to participate if they wish, by completing an anonymous questionnaire ensures different levels of involvement are possible. Furthermore, establishing whether female genital self-image, which can be reliably determined using a four-item questionnaire, is correlated with willingness to self-manage a pessary, may have clinical utility as it may help clinicians to target the intervention we plan to develop at those who are most likely to benefit from it.

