### 5.10 Quantitative phase data analysis

Data collected in the questionnaires will be analysed to provide descriptive statistics about the women who have completed the questionnaire, their experience of self-management and willingness to be interviewed in the qualitative phase. Free text data will also be analysed for the emergence of themes and coded to explore whether there are any patterns that emerge between women of similar characteristics with regards to willingness, or not, to self-manage a pessary. Statistical analysis will be performed by a statistician to test for correlation between demographics, patient characteristics and FGSIS-4 scores and willingness to self-manage a pessary for prolapse. Scores in the FGSIS-4 range between 4-16, with a mean score of 12 in a nationally representative population of over 2000 American women (Herbenick et al., 2011). Herbenick et al. (2011) have not determined a binary score for high and low FGSIS, however for the purpose of this study, a score of eight or less will indicate low FGSIS, whereas more than eight will indicate high FGSIS. To score eight or less, a participant must disagree with all four statements describing genital self-image therefore this is deemed to accurately represent FGSIS-4.

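### The 80% power in section 5.9 is not tied to the FGSIS-4 cut at 8; if the association is graded, the full score keeps that power with 90 women and the cut does not

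*Combined protocol and SAP*

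**What the plan says.** Section 5.9 chooses a generic medium effect because the relation between willingness and FGSIS-4 is unknown, and sizes the phase "for a chi squared test on a two by two table (self-management vs FGSIS"). It concludes: "With 5% significance level a sample of 90 will have 80% power to detect a medium effect size of 0.3". It gives no expected share of low scorers and no expected share of willing women.

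Section 5.10 defines the split: "a score of eight or less will indicate low FGSIS, whereas more than eight will indicate high FGSIS". It says the cited survey set no binary threshold, and justifies its own as follows: "To score eight or less, a participant must disagree with all four statements describing genital self-image". The only distributional figure is for the 4-16 range, "with a mean score of 12 in a nationally representative population of over 2000 American women".

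Section 5.10 also says a statistician is "to test for correlation between demographics, patient characteristics and FGSIS-4 scores and willingness to self-manage a pessary for prolapse". That wording does not exclude a test on the full score, but it does not say whether the full score or the split is the powered analysis. The table in 5.9 is labelled self-management, while 5.10 tests willingness.

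**The concern.** An effect of 0.3 on a two-by-two table is a statement about that particular table. When the table comes from cutting a score far out in one tail, few women fall in the low group. Phi is then bounded above, expected counts become small, and any graded relation in the score is diluted. The 80% is therefore not assured for the cut as defined.

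FGSIS-4 is the variable on which the sample size rests. Section 4.1 says "findings of the quantitative phase which affect willingness to self-manage a pessary can be explored in greater detail during interviews" and, of an FGSIS-4 correlation with willingness, "it may help clinicians to target the intervention we plan to develop at those who are most likely to benefit from it". A two-by-two test could miss an association that the score already collected would show, and that use would be lost.

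**Working it through.** **Inputs.** From 5.9: alpha 5%, n = 90, effect 0.3. From 5.10: range 4-16, cut at 8 or less, mean 12 (US women). Not in the documents, so assumed: SD 2 to 4, share willing (q) 30%, 50% or 70%.

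**1. The plan's own figure.** Noncentral chi-squared, 1 df, noncentrality n × w² = 90 × 0.09 = 8.1, gives power 81.2%. Required n = (1.960 + 0.842)² / 0.09 = 87.2, so 88 (80.4%). The stated 80% with 90 women reproduces, given phi = 0.3.

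**2. The reason for the cut.** Four items on a 4-16 scale imply items scored 1-4, with 3 or 4 meaning agree. Then 3 + 3 + 1 + 1 = 8 with two agree answers. Of 4⁴ = 256 answer patterns, 66 total 8 or less. Only 2⁴ = 16 of these have no agree answer, so 66 − 16 = 50 contain at least one. These are counts of patterns, not of women, but the claim that all four statements must be disagreed with is false.

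**3. How many low scorers.** For a rounded normal with mean 12, the share p at 8 or less is 4.0%, 8.1%, 12.2%, 15.9% and 19.1% for SD 2, 2.5, 3, 3.5 and 4: about 4 to 17 of 90 women.

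**4. Whether phi = 0.3 can occur.** With low scorers the less willing group, the maximum phi is √[p/(1−p) × q/(1−q)].
- q = 50%: 0.204, 0.296, 0.372, 0.434, 0.486
- q = 30%: 0.134 up to 0.318
- q = 70%: 0.312 up to 0.742

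Setting the formula to 0.3, phi = 0.3 needs p of at least 17.4% (16 women) at 30% willing, 8.3% (8) at 50% and 3.7% (4) at 70%. It is out of reach in 6 of the 15 settings, one of them narrowly (0.296). All expected counts reach 5 only with 10 low scorers at 50% willing (10 × 0.5 = 5) or 17 at 30% or 70% (17 × 0.3 = 5.1).

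**5. Power if the association is graded.** Samples of 90 were simulated with a score clipped to 4-16, its mean set to 12 and its SD as shown after clipping. Willingness follows a logistic curve whose slope makes the full-score correlation 0.3. Triplets are for 30 / 50 / 70% willing.

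| SD | Low share | Phi at cut | Full score, % | Chi-squared at cut, % | Fisher at cut, % |
|---|---|---|---|---|---|
| 2 | 4.1% | 0.10 / 0.13 / 0.16 | 83 / 83 / 83 | 1 / 17 / 35 | 1 / 10 / 22 |
| 2.5 | 8.8% | 0.14 / 0.17 / 0.20 | 84 / 83 / 83 | 17 / 37 / 47 | 10 / 27 / 41 |
| 3 | 13.6% | 0.18 / 0.20 / 0.22 | 85 / 84 / 82 | 37 / 49 / 56 | 31 / 43 / 52 |
| 3.5 | 18.2% | 0.21 / 0.23 / 0.24 | 85 / 83 / 81 | 51 / 56 / 61 | 45 / 51 / 53 |

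The Fisher-z formula agrees for the full score: Φ(atanh(0.3) × √87 − 1.96) = 82%. At the cut, 80% power would need 7.849/phi² women, which is 134 to 758 over the table. A probit curve with the unadjusted distribution of step 3 and SD up to 4 gives 82-85% on the full score, 1-61% for chi-squared and 1-54% for Fisher.

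**6. How much is due to this cut.** Any split costs power: cutting at 11 gives 65-71%. A lower mean narrows the gap. At SD 2.5 and 3, chi-squared at 8 has 39-59% at mean 11 and 54-65% at mean 10. Over the wider SD range it is about 25-64% and 50-68%. With half the women low it is 66-68%.

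**7. The reverse case.** If willingness differs only across the cut, with phi = 0.3, chi-squared has 79-95% and the full score 27-58% where that phi is attainable. At SD 3 and 50% willing the full-score correlation is 0.196, with 46.3% power against 88.1%.

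**The case against.** The strongest reply is that the comparison moves the effect. Section 5.9 states 0.3 for the two-by-two table; step 5 places it on the full score and derives a smaller phi. Under the effect as stated, where attainable, the cut has its 80% and is the better test. This stands as a condition on the result, and no passage settles whether the effect is graded or a step. But phi = 0.3 at this cut is demanding. With 13.6% low and 50% willing it means about 12% willing among low scorers against 56% among the rest. With 8.8% low it means about 2% against 55%.

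The proposed restatement still uses a conventional 0.3 with no data behind it. That is true, and 5.9 should keep saying so. The gain is that the value would refer to the analysis performed.

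The ranges rest on an assumed grid, the 1% is one sparse corner, and the US mean may not fit pessary users. All of this stands. Even so, the cut stayed below 80% in every graded setting tried, including an even split.

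Section 5.10 may already allow a full-score test, and the self-management label in 5.9 may be shorthand, since that section opens with willingness. Both points reduce the matter to naming the powered test.

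The consequence is modest. Section 4.1.1 calls the phase descriptive, the objectives in 3.2 do not include this test, and interview sampling needs only high and low groups.

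**Conclusion.** The concern holds. The calculation in 5.9 is correct for phi = 0.3, but the plan does not connect that value to the cut at 8. The sentence justifying the cut is false whatever the score distribution, and the plan offers no other evidence that an effect acts at 8. With mean 12, SD 2-4 and 30-70% willing, a graded full-score correlation of 0.3 gives 81-85% power on the full score and 1-61% by chi-squared at the cut. The size depends on the assumed SD and willing share, on a mean from US women and on a graded association; a true step at 8 reverses the order. This should be fixed because the change is cheap, but the effect on the study as a whole is limited.

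**What to change.** - In 5.9 and 5.10, name the powered analysis as willingness (yes/no) against the full FGSIS-4 score (4-16), by logistic regression or by point-biserial or rank correlation. Use willingness as the label in both sections.
- Restate the power in 5.9 as: 90 women give about 80% power for a correlation of 0.3 between the full FGSIS-4 score and willingness, 0.3 being a conventional value.
- Keep the cut at 8 for description and interview sampling. If it is tested, use Fisher's exact test and make no 80% claim for it.
- Correct the sentence that a total of 8 or less requires disagreement with every statement.

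The cost is a wording change in two sections, with no extra women or data. The simple two-by-two table is lost as the main test, and the full score is the weaker test if the effect acts only at the cut (27-58% against 79-95%).

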### 5.10 Quantitative phase data analysis

Data collected in the questionnaires will be analysed to provide descriptive statistics about the women who have completed the questionnaire, their experience of self-management and willingness to be interviewed in the qualitative phase. Free text data will also be analysed for the emergence of themes and coded to explore whether there are any patterns that emerge between women of similar characteristics with regards to willingness, or not, to self-manage a pessary. Statistical analysis will be performed by a statistician to test for correlation between demographics, patient characteristics and FGSIS-4 scores and willingness to self-manage a pessary for prolapse. Scores in the FGSIS-4 range between 4-16, with a mean score of 12 in a nationally representative population of over 2000 American women (Herbenick et al., 2011). Herbenick et al. (2011) have not determined a binary score for high and low FGSIS, however for the purpose of this study, a score of eight or less will indicate low FGSIS, whereas more than eight will indicate high FGSIS. To score eight or less, a participant must disagree with all four statements describing genital self-image therefore this is deemed to accurately represent FGSIS-4.

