### 5.3 Quantitative phase exclusion criteria

- Lacking capacity to give implied consent by completion of the questionnaire
- Has a first or preferred language that is not English
- Use a shelf, gell-horn or donut pessary

What affects willingness to self-manage a pessary? - Protocol Version 1.10 04.08.22

The convenience sample of women will be pessary using women who are attending a pessary clinic appointment in the women's outpatient department at Manchester University NHS Foundation Trust. While the limitations of a convenience sample are recognised, because such a large number of women attend the pessary clinic each week, it is anticipated that characteristics which may impact upon willingness to self-manage a pessary as identified in the scoping review such as pessary type, age, menopausal status, level of education, being sexually active, experience of pessary management and health status (Dwyer et al, 2022) will be represented within the sample (Gray and Grove, 2021).

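### No adjusted analysis is specified in section 5.10, so the plan cannot tell whether genital self-image (FGSIS-4) adds anything beyond age in explaining willingness to self-manage

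*Combined protocol and SAP*

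**What the plan says.** Section 5.10 has a statistician carry out analysis "to test for correlation between demographics, patient characteristics and FGSIS-4 scores and willingness to self-manage a pessary for prolapse". It names no method and no covariates. It also dichotomises the scale: "a score of eight or less will indicate low FGSIS, whereas more than eight will indicate high FGSIS".

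The one specific test is in section 5.9, where the sample size is calculated "for a chi squared test on a two by two table (self-management vs FGSIS". The text there adds: "With 5% significance level a sample of 90 will have 80% power to detect a medium effect size of 0.3". I read that table as willingness against FGSIS, because 5.9 opens with that relationship.

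The closing paragraph of section 5.3 lists characteristics that may bear on willingness and that the sample is expected to cover: "pessary type, age, menopausal status, level of education, being sexually active, experience of pessary management and health status". The baseline list in 5.7 includes year of birth, "Level of education" and "Self-management experience". It does not include menopausal status or sexual activity.

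Section 4.1 says that quantitative findings affecting willingness will be pursued in the interviews, with older age as its example. It adds that an FGSIS correlation may help clinicians to target the planned intervention.

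**The concern.** If older women, say, are both less willing to self-manage and lower on the FGSIS-4, willingness and FGSIS will be associated even if self-image has no influence of its own. The plan names age and education as possible influences and collects them, but specifies nothing that would separate them from FGSIS.

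At stake is what is passed on. An association that only reflects age could shape the interview questions and the choice of women to whom the intervention is offered. A clinician already knows the woman's age, so the practical question for targeting is whether FGSIS adds to it. An unadjusted test does not answer that.

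**Working it through.** **Inputs from the documents.** N = 90, 5% level, 80% power and effect size w = 0.3 (section 5.9); FGSIS-4 range 4 to 16, cited US mean 12, low group defined as 8 or less (section 5.10).

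**Inputs assumed.** The correlations of age with FGSIS and with willingness, the proportion scoring low, and the proportion willing. The documents give none of these.

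**Step 1: the plan's own figure.** For a chi-squared test on 1 df the non-centrality is N × w² = 90 × 0.09 = 8.1, which gives 81.2% power. The smallest N with 80% power is 88; the closed form is ((1.96 + 0.842)/0.3)² = 87.2. The stated 90 reproduces, for an unadjusted test.

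**Step 2: what a shared cause does, in simple form.** Take a binary confounder, with FGSIS and willingness independent given it, and all prevalences 50%. The induced correlation is the product of the two confounder correlations. At 0.4 and 0.4 it is 0.16, so the non-centrality is 90 × 0.16² = 2.3 and the test rejects in about 33% of studies. Simulation (40,000 studies per setting) gave:

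| Confounder with FGSIS / with willingness | Unadjusted chi-squared | Mantel-Haenszel, stratified on the confounder |
|---|---|---|
| 0.1 / 0.3 | 5.6% | 4.8% |
| 0.2 / 0.3 | 8.8% | 5.4% |
| 0.3 / 0.4 | 20.2% | 4.9% |
| 0.4 / 0.4 | 32.5% | 5.0% |
| 0.5 / 0.5 | 66.1% | 4.9% |

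FGSIS is binary in both columns, so adjustment alone restores the 5% level here. With weak confounding there is almost nothing to correct.

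**Step 3: closer to the plan.** Age, FGSIS and willingness are latent normal, and age has the same correlation r with both of the others. FGSIS has no effect of its own and n = 90. A cut at 8 against a cited mean of 12 suggests that fewer than half will score low, so 10% and 20% low are shown beside the median split.

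| Setting | r = 0.3 | r = 0.4 | r = 0.5 |
|---|---|---|---|
| Chi-squared, median splits | 8% | 16% | 33% |
| Chi-squared, 10-20% low, low scores aligned with the confounding | 7-8% | 11-14% | 19-28% |
| Chi-squared, 10% low, lowest across 30-50% willing | about 4% | about 6% | about 10% |
| Logistic, continuous FGSIS plus age | about 5% | about 5% | about 5% |

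The logistic row uses a continuous latent score, not the 4-to-16 integer total, and adjusts for the single true confounder. It is therefore a favourable case for adjustment.

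**Step 4: cost of adjusting.** If FGSIS shares a fraction R² of its variance with the covariates and its partial effect stays at 0.3, the effective N is about 90 × (1 − R²).

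- R² = 0.10: effective N is 81, non-centrality 81 × 0.09 = 7.29, power 77%.
- R² = 0.20: effective N is 72, non-centrality 72 × 0.09 = 6.48, power 72%.

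**Step 5: room in the model.** At ten women in the smaller willingness group per term, 50% willing gives 45/10 = 4.5, or four terms. At 30% willing it is 27/10 = 2.7, or two.

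**The case against.** The strongest reply is that this phase is descriptive. Section 4.1.1 calls it cross-sectional and descriptive, objective 1 in section 3.2 assigns the deeper understanding of factors to the interviews, and 5.11 gives the outputs as a summary and a basis for interview sampling. For targeting alone, an unadjusted association can be enough, and section 4.1 claims only a possible utility. That stands, and it keeps this to a cheap improvement. It does not remove the point, because section 4.1 also speaks of quantitative findings that affect willingness and sends them into the interviews.

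A reader might infer that the plan has chosen to test each characteristic one at a time. Section 5.10 does not say so and does not rule out a model; it is silent on adjustment.

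A reader might also take the median-split figures as the plan's error rate. The plan cuts at 8, and with a small low group the inflation is smaller and can vanish at r = 0.3.

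It is tempting to adjust for self-management experience as a matter of course, since it is collected. But experience may lie on the path from self-image to willingness, or follow from willingness, so adjusting for it could remove a real FGSIS effect.

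Finally, ten independent tests at 5% would give 1 − 0.95¹⁰ = 40% for at least one false positive. The plan states no number of tests and they would not be independent, so that figure is not evidence for the present point.

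**Conclusion.** The point holds as an omission: no adjusted analysis is specified, although age and education are named as possible influences and are collected. If age correlates 0.4 to 0.5 with both FGSIS and willingness, a purely age-driven association would be declared significant in roughly 11% to 33% of studies, taking the median split and the aligned 10-20% low groups together. An age-adjusted model would do so in about 5%. With weaker correlations, or a small low group and few willing women, the excess is slight or absent.

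The correlations and prevalences are assumptions. The documents do not support saying that an FGSIS association would be spurious, or that the sample-size arithmetic is wrong. The change is worth making because it needs no new data and serves both the targeting use and the explanatory use.

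**What to change.** Amend section 5.10 before the data are analysed:

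- Fit a logistic regression of willingness (binary, as the two-by-two table implies) on the FGSIS-4 total, kept continuous from 4 to 16. Report it unadjusted and adjusted for age from year of birth, with odds ratios and 95% CIs side by side.
- Add level of education, in few categories, only if the smaller willingness group allows it. State that rule in advance.
- Show adjustment for self-management experience only as a sensitivity analysis.
- Name the FGSIS term in the age-adjusted model as the main test, and label the other characteristics exploratory, reported as estimates with 95% CIs.

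This changes analysis wording only, with no new data or recruitment. The price is a wider adjusted interval (power about 77% or 72% at n = 90 if FGSIS shares 10% or 20% of its variance with the covariates and its partial effect stays at 0.3) and a limit of about two to four model terms. Menopausal status and sexual activity are not on the 5.7 list, so they cannot be adjusted for as the plan stands; this fix does not need them.
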